9.4. Safety Analyses

Safety analyses will be conducted using the safety population and summarized by treatment group as treated. The treatment emergent period will be defined as the period of time from the first dose date of the randomized study drug treatment through approximately 30 days after the last dose of study drug, or the date of initiation of another investigational agent or hormonal therapy affecting the hypothalamic-pituitary-gonadal axis or surgical intervention for uterine fibroids, or the date and time of the first dose of open-label extension (MVT-601-3003) study drug, whichever occurs first. Safety will be assessed through summaries of adverse events, the frequency of treatment discontinuations due to adverse events, laboratory evaluations, and bone densitometry results.

The severity of all adverse events is to be evaluated by the investigator based on the National Cancer Institute's CTCAE. All adverse events will be coded to preferred term and system organ

class using MedDRA 20.0 or higher. The incidence of adverse events will be presented by MedDRA system organ class and preferred term, relationship to study drug treatment, and severity. A patient reporting the same adverse event more than once is counted once, and at the maximum severity or strongest relationship to study drug treatment when calculating incidence.

Laboratory data consist of chemistry, hematology, and hormonal tests. Only data collected by the central laboratory will be used to do the analyses. The National Cancer Institute CTCAE, will be used to categorize toxicity grade for the laboratory parameters. Shift tables will be provided for each gradable parameter to summarize baseline toxicity grade versus post-baseline toxicity grade. For laboratory parameters that are not gradable by the CTCAE, a shift table based upon the normal range (low, normal, and high) will be provided for each parameter to summarize the baseline versus post-baseline results. All data will be listed and summarized by visit. The change from baseline to each post-baseline study visit will be presented by treatment group for each laboratory test.

For vital signs parameters, including temperature, all data will be listed and summarized by visit. The change from baseline to each post-baseline study visit will be presented by treatment group for each parameter.

ECGs will be read centrally. The distributions of corrected QT interval will be summarized at each visit. All data will be listed and summarized by visit. The change from baseline to each post-baseline study visit will be presented by treatment group for each ECG parameter.

Bone mineral density will be determined by the central radiology laboratory at the femoral neck, lumbar spine (L1-L4), and total hip. Values at Baseline, Week 12, and Week 24 visits will be summarized by treatment group along with the absolute and percent changes from Baseline and associated 95% confidence intervals. The number and percentage of patients meeting a bone mineral density decline of at least 7% by body area (lumbar, total hip, and femoral neck) will be presented with 95% confidence intervals by treatment group.

To support the inclusion of add-back therapy in the treatment regimen, the safety endpoint of mean percent change from Baseline in bone mineral density lumbar spine at Week 12 will be analyzed using pooled data from the two replicate studies (MVT-601-3001 and MVT-601-3002) with a formal comparison of Group A versus Group B (see details in the joint statistical analysis plan).

The incidence of vasomotor symptoms as assessed through adverse event reporting will be summarized by treatment arm.

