--	---

	
Safety Endpoints
 
 • Treatment-emergent adverse events, change in vital signs (including weight), clinical laboratory tests, and electrocardiograms; • Percent change from Baseline to Week 12 in bone mineral density at the lumbar spine (L1-L4) in Group A compared with Group B as assessed by DXA; • Percent change from Baseline to Week 24 in bone mineral density at the lumbar spine (L1-L4), total hip, and femoral neck as assessed by DXA; • Incidence of vasomotor symptoms.
	
Pharmacokinetic and Pharmacodynamic Endpoints
 
 • Pre-dose trough concentrations (C_t) of relugolix, estradiol, and norethindrone from Baseline through Week 24; • Changes from Baseline to Week 24 in pre-dose concentrations of LH, FSH, estradiol, and progesterone.
	
Exploratory Endpoint
 
 • Change from Baseline to Week 24 in the European Quality of Life Five-Dimension Five-Level scale comparing each relugolix treatment group to placebo inferentially and the two relugolix groups descriptively.
Statistical Methods	

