patients in each of the relugolix and placebo arms) will provide > 99% power to detect a difference of greater than 30 percentage points using a 2-sided test at significance level of 0.05. The total sample size for the study will be approximately 390 patients (130 patients in each of the 3 arms).

Safety

Safety assessments will include treatment-emergent adverse events, vital signs, physical examinations, clinical laboratory tests, 12-lead electrocardiograms, endometrial biopsies, and assessments of bone mineral density. Safety analyses will be based on all randomized patients who receive any amount of study drug (safety population). Drug exposure will be summarized by descriptive statistics. Severity of all treatment-emergent adverse events will be evaluated by the investigator based on the National Cancer Institute's Common Terminology Criteria for Adverse Events (CTCAE) and will be coded to preferred term, higher level term, and system organ class using the Medical Dictionary for Regulatory Activities (MedDRA). The number and percentage of patients with adverse events will be presented by MedDRA system organ class and preferred term, relationship to study drug, and severity. Descriptive statistics will be used rather than inferential statistics. Laboratory values also will be classified by toxicity grade based on the National Cancer Institute's CTCAE. Laboratory shift tables of the Baseline results to each of the subsequent visits will be produced. Bone mineral density will be evaluated in all patients at the lumbar spine (L1-L4), total hip, and femoral neck at the Baseline, Week 12, and Week 24 visits and the absolute, percent, and standardized changes from baseline will be summarized.

Vasomotor adverse events will be separately summarized.

A chartered independent Data and Safety Monitoring Board will monitor all available safety data, including bone density assessments, on an ongoing basis during this study.

Pharmacokinetics and Pharmacodynamics

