5.10.3. Prohibited Non-Drug Therapies

Surgical treatment of uterine fibroids and use of intrauterine devices are prohibited from the Screening 1 visit until the patient's final study visit unless urgently needed for patient safety.

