7.2.1. Adverse Event Reporting Period

Adverse events will be collected from the time the first dose of study drug is administered until the Follow-up visit approximately 30 days after the last dose of study drug or the date of initiation of another investigational agent or hormonal therapy affecting the hypothalamic-pituitary-gonadal axis or surgical intervention for uterine fibroids, whichever occurs first, as also specified in the study Schedule of Activities ([Section 1.1](#)). Study procedure-related adverse events will be collected from the signing of the informed consent form.

Serious adverse events will be collected from the signing of the informed consent form until the safety follow-up visit approximately 30 days after the last dose of study drug. Serious adverse events reported to the investigator after the safety reporting period should be reported to the sponsor if the investigator assesses the event as related to the study drug treatment.

With the exception of adverse events that are considered related to study screening procedures, (which are to be recorded as adverse events), events occurring between signing of the informed consent form and the first dose of study drug will be recorded as medical history and in the patient's clinical record for any patient who continues to meet eligibility criteria and proceeds to dosing with study drug.

Reporting instructions for serious adverse events are provided in [Section 7.6](#).

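### The therapy and surgery cut-offs in Section 9.4 are not limited to the time after the last dose, so a few women's adverse events on study drug could go uncollected or uncounted

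*Protocol*

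**What the plan says.** Section 9.4 opens the treatment-emergent period at the first dose of randomized treatment. It closes the period on the earliest of a list of dates. The list begins with about 30 days past the last dose, continues "or the date of initiation of another investigational agent or hormonal therapy affecting the hypothalamic-pituitary-gonadal axis or surgical intervention for uterine fibroids", goes on to the first dose of extension drug, and ends with "study drug, whichever occurs first. Safety will be assessed through summaries of adverse events". The hormonal trigger is restricted to "hormonal therapy affecting the hypothalamic-pituitary-gonadal axis or surgical intervention for uterine fibroids", so hormone use unrelated to that axis does not count.

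Section 7.2.1 ends the collection of non-serious adverse events at the Follow-up visit or at the start of another investigational agent or "hormonal therapy affecting the hypothalamic-pituitary-gonadal axis or surgical intervention for uterine fibroids, whichever occurs first". Table 1-1 footnote g does the same. For serious events the two places differ: footnote g repeats the therapy and surgery cut-off, while Section 7.2.1 collects up to the safety follow-up visit without it.

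The Synopsis names as a safety endpoint "Treatment-emergent adverse events, change in vital signs (including weight), clinical laboratory tests, and electrocardiograms". Section 9.4 takes the incidence of vasomotor symptoms, another safety endpoint, from adverse event reporting.

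Hormones for contraception are excluded throughout (Section 4.7), and progestins, estrogens and similar agents are on the prohibited list (Section 5.10.1). Section 5.10.3 bars fibroid surgery until the patient's "final study visit unless urgently needed for patient safety".

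**The concern.** The words about the last dose attach only to the 30-day limit. The therapy and surgery dates stand alone, and the earliest date wins. A programmer who follows the sentence as written would close the period on the day of an urgent operation or a prohibited hormone start, even if the woman goes on taking study drug. Her later adverse events would not be treatment-emergent. Under Section 7.2.1 and footnote g her non-serious events might never be recorded, and no later analysis plan can recover data that were not collected.

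Adverse events on study drug are the core of the safety comparison, and vasomotor events feed the argument for add-back therapy. A cut-off at these dates is sensible after treatment has ended, when a new therapy clouds attribution. During dosing it discards the very events that the period is meant to capture.

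**Working it through.** The plan gives no figure on this point, so the check is mainly of wording, followed by the size of the loss for one woman.

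**Step 1. The passages side by side.**

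| Place | What it governs | Ends at therapy or surgery date? | Limited to after last dose? |
|---|---|---|---|
| 9.4 | Treatment-emergent period | Yes | No |
| 7.2.1 | Non-serious event collection | Yes | No |
| Footnote g | Non-serious event collection | Yes | No |
| 7.2.1 | Serious event collection | No | Not applicable |
| Footnote g | Serious event collection | Yes | No |
| 6.5, footnote f | Timing of the Follow-up visit | Yes | Yes, by context |

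Section 6.5 and footnote f use the same dates only to bring forward a visit that assesses safety after treatment has stopped. That points to a post-treatment rule as the intention, but Section 9.4 does not carry the condition over.

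**Step 2. Can a trigger fall while study drug is being taken?** Section 5.10.3 itself provides for urgent surgery during the study. A hormone start would be a deviation, which a prohibition makes rare but not impossible. The Section 4.6 list of events leading to removal from therapy names neither. Its non-compliance item could cover a prohibited hormone, but it rests on judgement. Overlap is therefore possible.

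**Step 3. Loss for one woman.** Treatment lasts 24 × 7 = 168 days. With a trigger at Week w and dosing to Week 24, on-drug days lost = 168 − 7w.

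| Trigger week | On-drug days lost | Share of 168 days |
|---|---|---|
| 4 | 140 | 83% |
| 8 | 112 | 67% |
| 12 | 84 | 50% |
| 16 | 56 | 33% |
| 20 | 28 | 17% |

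The denominator is on-drug time. Section 6.4 expects most women to enter the extension, and Section 9.4 ends their period at the first extension dose, so a 30-day tail does not apply to them.

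**Step 4. Arm level, on assumed rates only.** The documents give neither trigger rates nor adverse event rates. Suppose a share r of 130 women trigger at a time spread evenly over Weeks 4 to 24, an average loss of 10 on-drug weeks. Weeks lost = 130 × r × 10, out of 130 × 24 = 3,120. At r = 1% this is 13 weeks (0.42%); at r = 10% it is 130 weeks (4.17%).

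For incidence, take the same true incidence p in Groups A and C and a constant hazard λ = −ln(1 − p)/T, with T = 24 + 30/7 weeks. Observed incidence = (1 − r)p + r × average of [1 − exp(−λt)] over t = 4 to 24. The spurious difference, A minus C, in percentage points is:

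| Assumed r in C / A | p = 10% | p = 30% | p = 60% |
|---|---|---|---|
| 1% / 1% | 0.00 | 0.00 | 0.00 |
| 2% / 0.5% | 0.07 | 0.21 | 0.37 |
| 5% / 1% | 0.20 | 0.56 | 0.99 |
| 10% / 2% | 0.40 | 1.12 | 1.97 |

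So the distortion runs from 0 to about 2 points, and nears 2 only in the most extreme corner of the assumptions.

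**The case against.** The strongest reply is that the situation should hardly arise. HPG-axis hormones are prohibited, women expected to have fibroid surgery within 6 months are ineligible (inclusion criterion 6), and surgery on study needs an urgent safety reason. A woman who breaks these rules may also be taken off study drug under the open-ended non-compliance item in Section 4.6. All of this stands, and it keeps the number of women small. It does not remove the gap, because urgent surgery is expressly allowed and removal is discretionary.

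A reader might infer that the loss falls unequally on the arms and biases the safety comparison. That is plausible, since women with continuing heavy bleeding may be likelier to need rescue, but no rate in the documents supports it. If placebo women did trigger more often, placebo events would be undercounted and relugolix would look worse, not safer.

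A reader might also infer that serious on-drug events can be hidden. Section 7.2.1 collects serious events with no therapy or surgery cut-off and asks for related ones even later, and Section 7.6 requires all serious events to be reported within 24 hours of site knowledge. Loss at collection follows only from footnote g. Under Section 7.2.1, what changes is whether the event appears in the treatment-emergent tables.

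Finally, a reader might think the whole safety analysis is cut short. Laboratory, vital-sign, ECG and bone density results are summarized by visit and are not stated to be limited to this period.

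**Conclusion.** The point holds as a defect of wording with a narrow reach. As written, Section 9.4 can close the treatment-emergent period during dosing, and Section 7.2.1 and footnote g can stop non-serious event collection at the same moment. The effect is confined to adverse event summaries, including vasomotor events. For an affected woman it is large: 140 to 28 on-drug days for a trigger at Weeks 4 to 20, if she continues to Week 24. For the trial it is probably small, because the triggers are prohibited. Its total size, and whether the arms differ, cannot be determined from the documents; the arm-level figures above are illustrations on assumed rates. Separately, footnote g and Section 7.2.1 contradict each other on when serious event collection ends, and that holds whatever the trigger rate.

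**What to change.** State in Section 9.4, Section 7.2.1 and Table 1-1 footnote g that the period covers all time from first through last dose of study drug. State there too that the start of another investigational agent, HPG-axis hormonal therapy or fibroid surgery truncates only the interval after the last dose. Reconcile the end date for serious event collection between Section 7.2.1 and footnote g. Flag in the listings any event that follows a hormonal start or surgery during treatment.

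The cost is one sentence in three places and one flag. The downside is that a few events confounded by the added therapy enter the tables, where the flag identifies them. No dosing or stopping rule changes.

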9.5. Pharmacokinetic and Pharmacodynamic Analyses

The PK concentration data (relugolix, estradiol [PK lab], and norethindrone) and serum pharmacodynamic data (LH, FSH, estradiol [central lab] and progesterone) will be listed and summarized descriptively by treatment arm and visit.

Plasma relugolix PK data will be combined with data from other phase 1 and phase 2 studies for population PK analysis. Full details will be provided in a separate Population PK SAP and reported separately. Plasma PK parameters of relugolix will be derived and summarized. The relationship between efficacy, safety, and exposure will be explored.

9.6. Exploratory Analyses

Descriptive summaries by treatment group and between treatment group comparisons (when applicable) will be provided for the following exploratory endpoint. Details on the endpoint analyses including deviations, handling of missing data, and statistical methods will be provided in the SAP. The following exploratory endpoint will be assessed:

- Change from Baseline to Week 24 in the European Quality of Life Five-Dimension Five-Level scale comparing each relugolix treatment group to placebo inferentially and the two relugolix groups descriptively.

9.7. Interim Analyses

There are no planned interim efficacy analyses.

10. RESPONSIBILITIES

10.1. Investigator Responsibilities

10.1.1. Good Clinical Practice

The investigator will ensure that this study is conducted in accordance with the principles of the “Declaration of Helsinki” (as amended in Edinburgh, Tokyo, Venice, Hong Kong, and South Africa), International Council on Harmonisation (ICH) guidelines, or with the laws and regulations of the country in which the research is conducted, whichever affords the greater protection to the study participant. For studies conducted under a United States investigational new drug application, the investigator will ensure that the basic principles of “Good Clinical Practice,” as outlined in 21 Code of Federal Regulations (CFR 312), subpart D, “Responsibilities of Sponsors and Investigators,” 21 CFR, part 50, 1998, and 21 CFR, part 56, 1998, are adhered to. These standards are consistent with the requirements of the European Community Directive 2001/20/EC.

Since this is a “covered” clinical study, the investigator will ensure that 21 CFR, Part 54, 1998, is adhered to; a “covered” clinical study is any “study of a drug or device in humans submitted in a marketing application or reclassification petition subject to this part that the applicant or FDA relies on to establish that the product is effective (including studies that show equivalence to an effective product) or that make a significant contribution to the demonstration of safety.” This requires that investigators and all sub-investigators must provide documentation of their financial interest or arrangements with the sponsor, or proprietary interests in the drug being studied. This documentation must be provided before participation of the investigator and any sub-investigator. The investigator and sub-investigator agree to notify the sponsor of any change in reportable interests during the study and for one year following completion of the study.

10.1.2. Institutional Review Board/Independent Ethics Committee Approval

This protocol and any accompanying material to be provided to the patient (such as advertisements, patient information sheets, or descriptions of the study used to obtain informed

consent) will be submitted by the investigator to an IRB or IEC. Approval from the IRB or IEC must be obtained before starting the study and should be documented in a letter to the investigator specifying the protocol number, protocol version, protocol date, documents reviewed, and date on which the committee met and granted the approval.

Any modifications made to the protocol after receipt of IRB or IEC approval must also be submitted to the IRB or IEC for approval before implementation.

10.1.3. Informed Consent

The investigator is responsible for obtaining written informed consent from each individual participating in this study after adequate explanation of the aims, methods, objectives, and potential hazards of the study and before undertaking any study-related procedures. The investigator must utilize an IRB- or IEC-approved informed consent form for documenting written informed consent that contains all elements required by national, state, local, and institutional regulations or requirements. Each informed consent form will be appropriately signed and dated by the patient.

10.1.4. Confidentiality

The investigator must assure that patients' anonymity will be strictly maintained and that their identities are protected from unauthorized parties. Only patient number, date of birth, and an identification code (ie, not names) should be recorded on any form or biological sample submitted to the sponsor, IRB or IEC, or laboratory. The investigator must keep a screening log showing codes, names, and addresses for all patients screened and for all patients enrolled in the study.

The investigator agrees that all information received from the sponsor, including but not limited to the IB, protocol, eCRFs and other study forms, the investigational drug, and any other study information, remain the sole and exclusive property of the sponsor during the conduct of the study and thereafter. This information is not to be disclosed to any third party (except employees or agents directly involved in the conduct of the study or as required by law) without prior written consent from the sponsor. The investigator further agrees to take all reasonable precautions to prevent the disclosure by any employee or agent of the study site to any third party or otherwise into the public domain.

10.1.5. Study Committees and Communication

There will be two formal committees for this study, a Steering Committee and a Data and Safety Monitoring Board.

The study will be overseen by a Steering Committee consisting of experts in the field of Women's Health and staff members of Myovant Sciences GmbH. The Steering Committee will participate in the design, conduct, analyses, and publication of the study. Steering Committee members will remain blinded to patients' treatment assignment and all unblinded data until the database is officially locked and unblinded.

An independent Data and Safety Monitoring Board will be established consisting of experts in women's health, clinical study safety monitoring, and statistics. This committee will evaluate the safety of study participants on an ongoing basis. Further details on the composition and responsibility of the Data and Safety Monitoring Board will be outlined in a separate charter.

10.1.6. Study Files and Retention of Records

The investigator must maintain adequate and accurate records to enable the conduct of the study to be fully documented and the study data to be subsequently verified. These documents should be classified into at least the following two categories:

- 1) Investigator's study file. The investigator's study file will contain the IB, protocol/amendments, IRB or IEC and governmental approval with correspondence, informed consent forms, drug records, staff curriculum vitae, authorization and training forms, and other appropriate documents and correspondence.
- 2) Patient clinical source documents. The required source data should include the following for each patient:
 - Patient identification (name, date of birth, gender);
 - Documentation that the patient meets eligibility criteria, (eg, history, physical examination, and confirmation of diagnosis to support inclusion and exclusion criteria);
 - Participation in the study (including study number);
 - Study discussed and date of informed consent;
 - Dates of all visits;
 - Documentation that protocol-specific procedures were performed;
 - Results of efficacy parameters, as required by the protocol;
 - Start and end date (including dose regimen) of study medication (drug dispensing and return should be documented as well);
 - Record of all adverse events and other safety parameters (start and end date, and causality and intensity as assigned by the investigator);
 - Concomitant medication (including start and end date); and
 - Date of study completion and reason for early discontinuation, if applicable.

All clinical study documentation must be retained by the investigator until at least 2 years after the last approval of a marketing application in an ICH region (ie, United States, Europe, or Japan) and until there are no pending or contemplated marketing applications in an ICH region; or, if no application is filed or if the application is not approved for such indication, until 2 years after the investigation is discontinued and regulatory authorities have been notified.

Investigators may be required to retain documents longer if required by applicable regulatory requirements, by local regulations, or by an agreement with the sponsor. The investigator must notify the sponsor before destroying any clinical study records.

Clinical study documentation includes the IB, signed protocol and amendments, signed informed consents, notification of serious adverse events and related reports, any dispensing and accountability logs, shipping records of investigational product and study-related materials, documentation of financial aspects of the study, insurance statement, and signed agreement between the involved parties, dated and documented IRB/IEC approval, approval of regulatory

authorities as applicable, decoding procedures for blinded studies, curriculum vitae and all training records of study site personnel, and all correspondence pertaining to the conduct of the study.

Should the investigator wish to assign the study records to another party or move them to another location, the sponsor must be notified in advance.

If the investigator cannot guarantee this archiving requirement at the study site for any or all of the documents, special arrangements must be made between the investigator and the sponsor to store these in sealed containers outside of the site so that they can be returned sealed to the investigator in case of a regulatory audit. When source documents are required for the continued care of the patient, appropriate copies should be made for storage outside of the site.

